8.6. Demographics and Baseline Characteristics

Demographics and baseline characteristics will be summarized using descriptive statistics for the Efficacy, Safety, and PK Analysis Sets by dose level of RC-P and route of administration (IM or IV).

Medical history will be listed. Prior medications and concomitant medications will be summarized.

8.7. Efficacy Analyses

8.7.1. Primary Efficacy Endpoint and Analysis

The primary efficacy endpoint of the study is the response rate, defined as the proportion of patients with the last 72-hour NSAA level ≥ 0.1 IU/mL during the first course of IM administration of RC-P. Patients in both Part A Cohort 1 and Cohort 2 at the final IM RC-P dose level will be included. Depending on the RC-P start day for a patient, this could be predose 4 if

the first course of RC-P started on a Monday; predose 6 if the first course of RC-P started on a Wednesday; or predose 5 if the first course of RC-P started on a Friday.

The primary efficacy endpoint will be estimated using the Efficacy Analysis Set for patients administered the final IM RC-P dose level with at least one 72-hour NSAA assessment collected within the protocol-defined sample collection window (± 2 hours) in Course 1 of Part A. The last observed 72-hour NSAA assessment collected within the protocol-defined sample collection window (± 2 hours) in Course 1 will be used in the calculation of the primary efficacy endpoint. Missing data will not be imputed. The response rate, along with the 95% Wald CI (confidence interval) will be provided. The primary efficacy endpoint will be met if the lower bound of the 95% CI of the response rate exceeds 90%.

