3.1.3.1. Part A (IM) Cohort 1, Determination for Possible Additional Patients/Cohorts

A target of 13 evaluable patients will be enrolled in each Cohort 1 subcohort. Evaluable patients for Cohort 1 are defined as patients who have received at least 3 doses of IM RC-P and have a 72-hour NSAA level (obtained within the ± 2 -hour window) during the second half of Course 1. For patients who are treated but are not evaluable, additional patients may be enrolled.

The SDRC ([Section 9.6](#)) will review the data when 6 evaluable patients in each subcohort (ie, Cohort 1a, Cohort 1b, Cohort 1c...Cohort 1x) complete Course 1. If 6 of the 6 evaluable patients in that subcohort have a 72-hour NSAA level ≥ 0.1 IU/mL and the safety/tolerability issues (described in [Section 3.1.3.3](#) Assessment of Safety/Tolerability in Part A Cohort 1) are acceptable based on a review by the SDRC, then the SDRC will also review the data when 13 evaluable patients in each subcohort complete Course 1. If 13 of the 13 (100%) evaluable patients in that subcohort have 72-hour NSAA levels ≥ 0.1 IU/mL and the safety/tolerability issues are acceptable based on a review by the SDRC, no additional patients will be enrolled in Cohort 1. Patients will be enrolled at this IM RC-P dose level in Part A Cohort 2 of this study.

If 1 or more of the 13 evaluable patients in the subcohort has a 72-hour NSAA level < 0.1 IU/mL, or if any safety/tolerability issues are not acceptable based on a review by the SDRC, then the PK and safety data will be analyzed to determine whether a new subcohort (with a lower dose, higher dose, or different doses on different days) is needed.

Based on all of the data, the SDRC may recommend that a different dose be given on Fridays than on Mondays and Wednesdays. Any additional dose level(s) studied for RC-P will not exceed a 50% increase from the previous dose level.

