5.4. Method of Assigning Patients to Treatments

This is an open-label study with only one study treatment (RC-P).

5.5. Dose Modifications for Safety/Tolerability Issues**5.5.1. Systemic Allergic Reaction/Anaphylaxis**

- Discontinue RC-P if the patient develops \geq Grade 3 allergic reaction/hypersensitivity

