8.4. Analysis Sets and Handling of Dropouts

- Enrolled Analysis Set will include patients who signed the informed consent and meet inclusion/exclusion criteria per Investigator
- Safety Analysis Set will include patients who received at least one dose of RC-P
- Efficacy Analysis Set will include patients who received at least one dose of RC-P and have at least one 48- or 72-hour NSAA assessment collected within the protocol-defined sample collection window (± 2 hours) in Course 1
- PK Analysis Set will include patients who received at least one dose of RC-P and have at least one postdose evaluable SAA or PK concentration value
- PD Analysis Set will include patients who received at least one dose of RC-P and have at least one postdose evaluable L-asparagine or L-glutamine value

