Abbreviations: ADA = anti-RC-P antibodies; AE = adverse event; ALT = alanine aminotransferase; aPTT = activated partial thromboplastin time; AST = aspartate aminotransferase; ATIII = antithrombin III activity and antigen; CBC = Complete Blood Count; EOS = end of study; Fg = fibrinogen; IM = intramuscular; IV = intravenous; PD = pharmacodynamic; PK = pharmacokinetic; PT = prothrombin time; RC-P = Recombinant Crisantaspase produced in *Pseudomonas fluorescens*; WBC = white blood cells.

RC-P

Jazz Pharmaceuticals Ireland Limited

Protocol Amendment 02: JZP458-201

APPENDIX 2. PART A/PART B PHARMACOKINETIC, PHARMACODYNAMIC, AND IMMUNOGENICITY SAMPLING SCHEDULE FOR IM OR IV RC-P PATIENTS

M/W/F Course 1	RC-P Dosing Cohorts	Day	1 (M)	3 (W)	5 (F)	8 (M)	10 (W)	12 (F)	EOS
			Dose 1	Dose 2	Dose 3	Dose 4	Dose 5	Dose 6	-
		PK (SAA)	0h (predose 1); 2.5h postdose 1 ^a	48h postdose 1 (predose 2)	48h postdose 2 (predose 3)	72h postdose 3 (predose 4), 2.5h postdose 4 ^a	48h postdose 4 (predose 5)	48h postdose 5 (predose 6)	-
		PK (Content) ^b	0h (predose 1); 2.5h postdose 1 ^a	48h postdose 1 (predose 2)	48h postdose 2 (predose 3)	72h postdose 3 (predose 4), 2.5h postdose 4 ^a	48h postdose 4 (predose 5)	48h postdose 5 (predose 6)	-
		PD (Asparagine, Glutamine)	0h (predose 1); 2.5h postdose 1 ^a	48h postdose 1 (predose 2)	48h postdose 2 (predose 3)	72h postdose 3 (predose 4), 2.5h postdose 4 ^a	48h postdose 4 (predose 5)	48h postdose 5 (predose 6)	-
		ADA ^c	0h (predose 1)	-	-	-	-	48h postdose 5 (pre-dose 6)	-
		PK (SAA)	0h (predose 1)	-	-	72h postdose 3 (predose 4)	-	48h postdose 5 (pre-dose 6)	EOS ^d
		PK (Content) ^b	0h (predose 1)	-	-	72h postdose 3 (predose 4)	-	48h postdose 5 (pre-dose 6)	EOS ^d
		PD (Asparagine, Glutamine)	0h (predose 1)	-	-	72h postdose 3 (predose 4)	-	48h postdose 5 (predose 6)	EOS ^d
		ADA ^c	0h (predose 1)	-	-	-	-	-	EOS ^d
		Day	1 (W)	3 (F)	6 (M)	8 (W)	10 (F)	13 (M)	EOS
		RC-P Dosing Cohorts	Dose 1	Dose 2	Dose 3	Dose 4	Dose 5	Dose 6	-
		PK (SAA)	0h (predose 1); 2.5h postdose 1 ^a	48h postdose 1 (predose 2)	72h postdose 2 (predose 3)	48h postdose 3 (predose 4), 2.5h postdose 4 ^a	48h postdose 4 (predose 5)	72h postdose 5 (predose 6)	-
		PK (Content) ^b	0h (predose 1); 2.5h postdose 1 ^a	48h postdose 1 (predose 2)	72h postdose 2 (predose 3)	48h postdose 3 (predose 4), 2.5h postdose 4 ^a	48h postdose 4 (predose 5)	72h postdose 5 (predose 6)	-

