		PD (Asparagine, Glutamine)	0h (predose 1); 2.5h postdose 1 ^a	48h postdose 1 (predose 2)	72h postdose 2 (predose 3)	48h postdose 3 (predose 4), 2.5h postdose 4 ^a	48h postdose 4 (predose 5)	72h postdose 5 (predose 6)	-
		ADA ^c	0h (predose 1)	-	-	-	-	72h postdose 5 (predose 6)	-

RC-P
Protocol Amendment 02: JZP458-201

		PK (SAA)	0h (predose 1)	-	-	-	48h postdose 4 (predose 5)	72h postdose 5 (predose 6)	EOS ^d
Subsequent Courses (for both Cohorts 1 & 2)		PK (Content) ^b	0h (predose 1)	-	-	-	48h postdose 4 (predose 5)	72h postdose 5 (predose 6)	EOS
		PD	0h (predose 1)	-	-	-	48h postdose 4 (predose 5)	72h postdose 5 (predose 6)	EOS ^d
		ADA ^c	0h (predose 1)	-	-	-	-	-	EOS ^d
F/M/W	RC-P Dosing	Day	1 (F)	4 (M)	6 (W)	8 (F)	11 (M)	13 (W)	EOS
Course 1	C o h o r t s		Dose 1	Dose 2	Dose 3	Dose 4	Dose 5	Dose 6	
		PK (SAA)	0h (predose 1); 2.5h postdose 1 ^a	72h postdose 1 (predose 2)	48h postdose 2 (predose 3)	48h postdose 3 (predose 4), 2.5h postdose 4 ^a	72h postdose 4 (predose 5)	48h postdose 5 (predose 6)	-
		PK (Content) ^b	0h (predose 1); 2.5h postdose 1 ^a	72h postdose 1 (predose 2)	48h postdose 2 (predose 3)	48h postdose 3 (predose 4), 2.5h postdose 4 ^a	72h postdose 4 (predose 5)	48h postdose 5 (predose 6)	-
		PD (Asparagine, Glutamine)	0h (predose 1); 2.5h postdose 1 ^a	72h postdose 1 (predose 2)	48h postdose 2 (predose 3)	48h postdose 3 (predose 4), 2.5h postdose 4 ^a	72h postdose 4 (predose 5)	48h postdose 5 (predose 6)	-
		ADA ^c	0h (predose 1)	-	-	-	-	48h postdose 5 (predose 6)	-
Subsequent Courses (for both Cohorts 1 & 2)		PK (SAA)	0h (predose 1)	-	-	-	72h postdose 4 (predose 5)	48h postdose 5 (predose 6)	EOS ^d
		PK (Content) ^b	0h (predose 1)	-	-	-	72h postdose 4 (predose 5)	48h postdose 5 (predose 6)	EOS ^d
		PD	0h (predose 1)	-	-	-	72h postdose 4 (predose 5)	48h postdose 5 (predose 6)	EOS ^d
		ADA ^c	0h (predose 1)	-	-	-	-	-	EOS ^d

^a The sampling schedule for IM and IV RC-P drug administration is the same except that the 2.5 hour postdose sample is only collected for IM administration; for IV administration, an end of infusion sample is collected at approximately 2 hours post the start of infusion.

^b PK (Content) is the same as serum asparaginase concentration.

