#### **9.1.2. Analysis of the Primary Efficacy Endpoint**

The primary efficacy endpoint will be estimated using the Efficacy Analysis Set for patients administered the final IM RC-P dose level with at least one 72-hour NSAA assessment collected within the protocol defined sample collection window ( $\pm 2$  hours) in Course 1 of Part A. The last observed 72-hour NSAA assessment collected within the protocol defined sample collection window ( $\pm 2$  hours) in Course 1 will be used in the calculation of the primary efficacy endpoint. Missing data will not be imputed. The response rate, along with the 95% Wald CI will be provided. The primary efficacy endpoint will be met if the lower bound of the 95% CI of the response rate exceeds 90%.

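### Patients who stop RC-P early are scored or excluded from the primary endpoint according to start weekday, and no planned analysis counts the early stop as a failure

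*Protocol*

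**What the plan says.** Protocol 8.7.1 takes the response from "The last observed 72-hour NSAA assessment collected within the protocol-defined sample collection window" in Course 1, among "patients administered the final IM RC-P dose level with at least one 72-hour NSAA assessment collected within the protocol-defined sample collection window". SAP 9.1.2 repeats the rule: "The last observed 72-hour NSAA assessment collected within the protocol defined sample collection window". Both say that missing data are not imputed. The parent Efficacy Analysis Set (protocol 8.4) admits "patients who received at least one dose of RC-P and have at least one 48- or 72-hour NSAA assessment collected" in window, so one dose is enough to enter.

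The endpoint definition names a sample for each start day: predose 4 for Monday, predose 6 for Wednesday and predose 5 for Friday. The wording presents these as possibilities rather than requirements.

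Protocol Appendix 2 schedules these 72-hour samples in Course 1:
- Monday start: one, after dose 3.
- Wednesday start: two, the first listed as "72h postdose 2 (predose 3", the second after dose 5.
- Friday start: two, the first listed as "72h postdose 1 (predose 2", the second after dose 4.

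Cohort 1 evaluability (protocol 3.1.3.1) is stricter. It counts "patients who have received at least 3 doses of IM RC-P and have a" 72-hour level from the second half of Course 1.

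Protocol 5.5.1 is one route to early stopping: "Discontinue RC-P if the patient develops" an allergic reaction of Grade 3 or higher. The only sensitivity analysis of the primary endpoint, SAP 9.1.3, concerns samples missed because of COVID-19.

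**The concern.** A Wednesday or Friday starter who stops before the named sample may already have a first-week 72-hour value, and that value becomes the response. A Monday starter with the same clinical course may have no 72-hour value and is left out. Start day follows the patient's planned chemotherapy schedule, so an administrative feature decides how an early stop is scored.

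Protocol 8.5 treats missing data as missing completely at random. Yet protocol 1.1 describes hypersensitivity as the prominent dose-limiting reaction to asparaginases and says antibodies may interfere with the therapeutic effect. A reaction on repeat dosing can both end treatment and remove the later sample. A value taken after one or two doses says little about activity after that reaction.

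At stake is a single-arm success criterion with a small allowance for failures. It is applied at an interim analysis that stops enrollment to the cohort if it is met (protocol 3.1.1) and again at the primary analysis.

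**Working it through.** **1. Which sample is scored.** This follows from the Appendix 2 schedule and the last-observed rule. It assumes that a 72-hour sample due after the last dose received is still drawn in window.

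| Doses received | Monday start | Wednesday start | Friday start |
|---|---|---|---|
| 1 | none, excluded | none, excluded | after dose 1 |
| 2 | none, excluded | after dose 2 | after dose 1 |
| 3 | after dose 3 | after dose 2 | after dose 1 |
| 4 | after dose 3 | after dose 2 | after dose 4 |
| 5 or 6 | after dose 3 | after dose 5 | after dose 4 |

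Exclusion against inclusion is therefore the difference for stops after 1 or 2 doses. For later stops the difference is how early the scored sample was taken. The same fallback applies to a Wednesday or Friday starter who stays on RC-P but whose later 72-hour sample is missing or out of window.

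**2. The plan's own figures.** The criterion is p − 1.96·√(p(1−p)/n) > 0.90.
- Primary: n = 98 × 0.95 ≈ 93. The smallest passing count is 88, and P(X ≥ 88 | 93, 0.96) = 0.831, against 83% stated. With a true rate of 94% it is 0.512, against 51% stated.
- Interim: n = 48. The smallest passing count is 46, and P(X ≥ 46 | 48, 0.96) = 0.699, against 70% stated.

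The stated probabilities reproduce.

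**3. Room in the criterion.**
- 88/93: 0.9462 − 1.96 × 0.0234 = 90.04%, pass. 87/93: 88.6%, fail. So 5 non-responders are allowed.
- 46/48: 90.2%, pass. 45/48: 86.9%, fail. So 2 are allowed.

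**4. Illustration.** Neither document gives the early-stopping rate or the start-day split, so the number k of early stoppers among the 93 is an assumption. The other 93 − k respond at 96%.
- Scored as responders on an early value: P(X ≥ 88 − k | 93 − k, 0.96).
- Scored as non-responders: P(X ≥ 88 | 93 − k, 0.96).

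| k | As responders | As non-responders |
|---|---|---|
| 0 | 0.831 | 0.831 |
| 1 | 0.837 | 0.692 |
| 2 | 0.843 | 0.504 |
| 3 | 0.848 | 0.297 |

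**5. Is it handled elsewhere?** Protocol 8.5 defers missing PK concentrations to the SAP. SAP 7.2.5 points to Section 11, which contains no rule for them. SAP 9.1.3 addresses COVID-19 only.

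**The case against.** The strongest reply is that the rule applies its own definition. The endpoint is the last 72-hour value in Course 1, the named samples are not binding, and a real in-window observation is used. A reader might infer a conflict with the statement that missing data are not imputed. The documents do not support that, because nothing is imputed.

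A reader might also infer that the rule turns failures into successes and so must bias the rate upward. That goes too far. An early value below 0.1 IU/mL is scored as non-response and stays in. Restricting the analysis to the named sample would drop that patient and could raise the rate.

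Nor does removing early-value patients readily reverse a result. Suppose 5% of 98 (about 5) lack the named sample and start days are evenly spread. About 3 of the 5 then stay in on an early value, 2 leave, and n = 96. The most marginal pass is 91/96 (lower bound 90.35%). Removing those 3 as responders leaves 88/93 (90.04%), which still passes. If the analysed number fell below 93 or 48, protocol 8.3 would require more enrollment.

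Other parts of the plan give some visibility. SAP 11 summarises the proportion at or above 0.1 IU/mL by time, and safety tables report discontinuations for adverse events. Cohort 1 evaluability serves dose selection, so a different evaluable set is not in itself a contradiction.

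These replies limit the size and direction of the effect. They leave the weekday asymmetry, and none supplies an analysis in which stopping early for an adverse event counts as failure.

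**Conclusion.** The point stands as a gap in the handling of early stopping. Some patients are scored on a sample taken after 1 or 2 doses, others with the same number of doses are excluded, and the start weekday decides which. The early stop itself never counts as failure. The primary analysis is also looser than the evaluability standard under which the dose is chosen.

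The size cannot be derived from the documents. With 5 non-responders allowed in 93 and 2 in 48, a few such patients could decide the result if scored as non-responders. With 3 of them, and a 96% response among the rest, the probability of success is 0.848 when they are scored as responders and 0.297 when scored as non-responders.

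The documents do not show that the response rate will be overstated or that the planned conclusion would change, and no stated power figure is wrong. The gap should be closed with supporting analyses.

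**What to change.** Add to SAP 9.1.3, for both the interim and the primary analysis:

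- (a) A sensitivity analysis, applied identically to all start days, counting as a non-responder every patient at the final IM dose who stopped RC-P for an adverse event before the named 72-hour sample (predose 4, 6 or 5 for Monday, Wednesday or Friday). It must include those with no 72-hour sample, so the denominator is wider than in the primary analysis.
- (b) A sensitivity analysis restricted to the named second-half sample.
- (c) The number of patients scored on an earlier 72-hour value, by start day.

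Do not make the restriction in (b) the sole primary rule without (a), because it drops early non-responders as well as early responders. Some asymmetry remains even under (a), since the named sample follows dose 3, 5 or 4 depending on start day. The count in (c) lets the reader judge how much the fallback matters.

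The cost is SAP wording, one or two extra tables and a possibly less favourable supporting estimate. No new samples are needed.

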8.7.2. Secondary Efficacy Endpoints and Analyses

Secondary efficacy endpoints include the following from Part A of the study:

- Key secondary efficacy endpoint: Proportion of patients with the last 48-hour NSAA level ≥ 0.1 IU/mL during the first course of IM administration of RC-P
- Proportion of patients with the last 48-hour level ≥ 0.4 IU/mL during the first course of IM administration of RC-P
- Proportion of patients with the last 72-hour NSAA level ≥ 0.4 IU/mL during the first course of IM administration of RC-P

8.7.2.1. Key Secondary Efficacy Endpoint: Proportion of Patients with the Last 48-hour NSAA Level ≥ 0.1 IU/mL during the First Course of IM Administration of RC-P

The proportion of patients with the last 48-hour NSAA level ≥ 0.1 IU/mL during the first course of IM administration of RC-P will be analyzed using the same methodology as the primary efficacy endpoint using the Efficacy Analysis Set for patients administered the final IM RC-P dose level with at least one 48-hour NSAA assessment collected within the protocol-defined sample collection window (± 2 hours) in Course 1 of Part A. The response rate, along with the 95% Wald CI will be provided.

8.7.2.2. Proportion of Patients with the Last 48-hour NSAA Level ≥ 0.4 IU/mL during the First Course of IM Administration of RC-P

The proportion of patients with the last 48-hour NSAA level ≥ 0.4 IU/mL during the first course of IM administration of RC-P will be analyzed. This analysis will use the same methodology as the primary efficacy endpoint using the Efficacy Analysis Set for patients administered the final IM RC-P dose level with at least one 48-hour NSAA assessment collected within the protocol-defined sample collection window (± 2 hours) in Course 1 of Part A. The response rate, along with the 95% Wald CI will be provided.

8.7.2.3. Proportion of Patients with the Last 72-hour NSAA Level ≥ 0.4 IU/mL during the First Course of IM Administration of RC-P

The proportion of patients with the last 72-hour NSAA level ≥ 0.4 IU/mL during the first course of IM administration of RC-P will be analyzed. This analysis will use the same methodology as the primary efficacy endpoint using the Efficacy Analysis Set for patients administered the final

IM RC-P dose level with at least one 72-hour NSAA assessment collected within the protocol-defined sample collection window (± 2 hours) in Course 1 of Part A. The response rate, along with the 95% Wald CI will be provided.

8.7.3. Exploratory Efficacy Endpoints and Analyses

Exploratory efficacy endpoints include the following from Part B of the study:

- Proportion of patients with the last 48-hour NSAA level ≥ 0.1 IU/mL during the first course of IV administration of RC-P
- Proportion of patients with the last 72-hour NSAA level ≥ 0.1 IU/mL during the first course of IV administration of RC-P
- Proportion of patients with the last 48-hour NSAA levels ≥ 0.4 IU/mL during the first course of IV administration of RC-P
- Proportion of patients with the last 72-hour NSAA level ≥ 0.4 IU/mL during the first course of IV administration of RC-P

8.7.3.1. Proportion of Patients with the Last 48-hour NSAA Level ≥ 0.1 IU/mL during the First Course of IV Administration of RC-P

The proportion of patients with the last 48-hour NSAA level ≥ 0.1 IU/mL during the first course of IV administration of RC-P will be analyzed. This analysis will use similar methodology as the primary efficacy endpoint using the Efficacy Analysis Set for patients administered the final IV RC-P dose level in Part B with at least one 48-hour NSAA assessment collected within the protocol-defined sample collection window (± 2 hours) in Course 1. The response rate, along with the 95% CI will be provided.

8.7.3.2. Proportion of Patients with the Last 72-hour NSAA Level ≥ 0.1 IU/mL during the First Course of IV Administration of RC-P

The proportion of patients with the last 72-hour NSAA level ≥ 0.1 IU/mL during the first course of IV administration of RC-P will be analyzed. This analysis will use similar methodology as the primary efficacy endpoint using the Efficacy Analysis Set for patients administered the final IV RC-P dose level in Part B with at least one 72-hour NSAA assessment collected within the protocol-defined sample collection window (± 2 hours) in Course 1. The response rate, along with the 95% CI will be provided.

8.7.3.3. Proportion of Patients with the Last 48-hour NSAA Level ≥ 0.4 IU/mL during the First Course of IV Administration of RC-P

The proportion of patients with the last 48-hour NSAA level ≥ 0.4 IU/mL during the first course of IV administration of RC-P will be analyzed. This analysis will use similar methodology as the primary efficacy endpoint using the Efficacy Analysis Set for patients administered the final IV RC-P dose level in Part B with at least one 48-hour NSAA assessment collected within the protocol-defined sample collection window (± 2 hours) in Course 1. The response rate, along with the 95% CI will be provided.

8.7.3.4. Proportion of Patients with the Last 72-hour NSAA Level \geq 0.4 IU/mL during the First Course of IV Administration of RC-P

The proportion of patients with the last 72-hour NSAA level \geq 0.4 IU/mL during the first course of IV administration of RC-P will be analyzed. This analysis will use similar methodology as the primary efficacy endpoint using the Efficacy Analysis Set for patients administered the final IV RC-P dose level in Part B with at least one 72-hour NSAA assessment collected within the protocol-defined sample collection window (\pm 2 hours) in Course 1. The response rate, along with the 95% CI will be provided

